5.10 Criteria for Taking a Participant Off Study

Safety Run-In and Randomized Treatment:

Participants will be removed from study (including study follow-up) when any of the following criteria apply:

- Lost to follow-up
- Withdrawal of consent for data submission
- Death

The reason for taking a participant off study, and the date the participant was removed, must be documented in the case report form (CRF). In addition, the study team will ensure the participant's status is updated in OnCore in accordance with [REGIST-OP-1](#).

5.11 Requests for Unblinding

Only applicable for Randomized Treatment:

Requests for unblinding may be granted under the following circumstances

1. Emergency unblinding- If there is a serious adverse event or other severe illness and the study drug is suspected to be a factor, a request for unblinding may be submitted to the study team/pharmacy. It is preferable that the decision to unblind is discussed with the Principal Investigator, but the treating investigator holds the final authority to request emergency unblinding to protect the safety of participants. The study team will contact the pharmacy to facilitate unblinding.
 - a. Contact #1 for Emergency Unblinding:
[name] – Research Manager
[contact] // [contact]
[contact]
 - b. Contact #3 for Emergency Unblinding:
DFCI CRC General Inbox
[contact]

24-hour contact for emergency unblinding:

[name]

Pager: Call [contact] for beeper # [name]

2. Elective unblinding – Patients or their treating investigators who would like to know if they have received troriluzole or not may request unblinding from the study team on Day 365. Unblinding will be facilitated by the study team members:
 - a. [name] – Study Coordinator
[contact] // [contact]
[contact]
 - b. [name] – Research Manager
[contact] // [contact]
[contact]

3. Final Unblinding

The official, final database will not be unblinded until medical/scientific review has been performed, protocol deviations have been identified, and data have been declared final and complete.

The final unblinding will include distribution of a subject letter to participants and subject treatment information to study investigators. Final unblinding will occur after enrollment has been completed and the Sponsor-Investigator has determined that study data are final and complete.

A planned futility interim analysis will be conducted during the randomized trial. Blinding to treatment assignment will be maintained at all investigational sites at the time of the futility analysis. The unblinded results of interim analyses will not be shared with the investigators prior to the completion of the study. Subject-level unblinding will be restricted to an unblinded statistician and scientific programmer performing the futility analysis.

The Sponsor-Investigator will serve as the primary reviewer of the results of the interim analysis and will follow the protocol-defined guidance in making a decision on discontinuation of the study or modification.

Subject Letter.

At the close of the trial after unblinding, a letter is to be sent by the investigator to those subjects who received placebos or investigational product to provide information on the trial and include the following advice:

“You have participated in a trial conducted by Dana-Farber Cancer Institute under the sponsorship of Biohaven Pharmaceuticals. This is to advise you that you were among those who received a look-alike capsule created by the Sponsor to resemble the study drug troriluzole as much as possible. You did not receive the active drug troriluzole as manufactured by Biohaven Pharmaceuticals.”

Or

“You have participated in a trial conducted by Dana-Farber Cancer Institute under the sponsorship of Biohaven Pharmaceuticals. This trial included participants that received active drug and participants that received a look-alike capsule created by the Sponsor to resemble the study drug and act as a placebo. This is to advise you that you were among those who received the active drug troriluzole as manufactured by Biohaven Pharmaceuticals.”

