12.2 Data Safety Monitoring

12.2.1 The DF/HCC Data and Safety Monitoring Board (DSMB) will review and monitor study progress, toxicity, safety and other data from the randomized portion of this study. The Board is chaired by a medical oncologist from outside of DF/HCC and its membership composed of internal and external institutional representation. Information that raises any questions about participant safety or protocol performance will be addressed by the Sponsor-Investigator, statistician and study team. Should any major concerns arise, the DSMB will offer recommendations regarding whether or not to suspend the study.

The DSMB will meet twice a year to review accrual, toxicity, response and reporting information. Information to be provided to the DSMB may include: participant accrual; treatment regimen information; all adverse events and serious adverse events reported across all sites by category; summary of any deaths on study; audit results; and a summary provided by the study team. Other information (e.g. scans, laboratory values) will be provided upon request.

12.2.2 The DF/HCC Data Safety Monitoring Committee (DSMC) will review and monitor study progress, toxicity, safety and other data from the safety run-in phase of this study. The DSMC meets monthly to review protocols and is chaired by a medical oncologist appointed by the Senior VP for Research. The DSMC will typically review a protocol every 3, 6, or 9 months based on protocol specifics. Information that raises any questions about participant safety or protocol performance will be addressed by the Sponsor-Investigator, statistician and study team. Should any major safety concerns or issues with data compliance arise, the DSMC will offer recommendations regarding whether or not to suspend the study.

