13.4 Interim Monitoring Plan

Safety Run-in: The DLT observation period is 6 weeks. After all patients in a dose cohort have been followed for 6 weeks or had dose-limiting toxicity (DLT), enrollment will pause for review of the safety data. The safety reviews will decide whether to declare an MTD and proceed with the randomized trial, adjust the dose, or stop enrollment.

Early stopping rule for futility: An interim look for futility will take place when approximately 45 patients have been enrolled and treated on the Phase II portion of the trial (a total of 15 PFS events have occurred). A proportional hazards mixture cure model (Section 13.5) will be fit to the data at the time of the interim analysis and will be stratified by the randomization factors; randomized treatment will be the only predictor in this model. If the observed hazard ratio (INT vs. INP) from the latency portion of the model is 0.96 or larger then study enrollment will stop and the trial will cease due to futility.

Early stopping rule for neurotoxicity: Sequential boundaries will be used to monitor the rate of neurotoxicity (Section 7.3 Adverse Event Reporting) in the first 45 patients enrolled and treated in the Phase II portion of the trial. Accrual will be halted if excessive numbers of neurotoxicities are seen, that is, if the number of neurotoxicities is equal to or exceeds b_n out of n patients (see table). This is a Pocock-type stopping boundary that yields the probability of crossing the boundary = 0.1 when the rate of neurotoxicity is equal to 0.20.⁴³ Accrual will be halted if the number of neurotoxicities is equal to or exceeds b_n out of n patients, and the DSMB or DSMC may permanently stop the trial.

Table for neurotoxicity stopping rule:

Number of Patients, n	1	2	3	4	5	6	7	8	9	10	11	12	13	14	15	16	17	18	19	20	
Boundary, b_n	-	-	3	3	4	4	5	5	5	6	6	6	7	7	7	7	8	8	8	9	
Number of Patients, n	21	22	23	24	25	26	27	28	29	30	31	32	33	34	35	36	37	38	39	40	
Boundary, b_n	9	9	9	10	10	10	11	11	11	11	12	12	12	12	13	13	13	13	14	14	
Number of Patients, n	41	42	43	44	45																
Boundary, b_n	14	14	15	15	15																

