2.1 External Site

An External Site is an institution that is outside the DF/HCC and DF/PCC consortium that is collaborating with DF/HCC on a protocol where the sponsor is a DF/HCC investigator. The External Site acknowledges the DF/HCC Sponsor as having the ultimate authority and responsibility for the overall conduct of the study.

Each External Site is expected to comply with all applicable DF/HCC requirements stated within this Data and Safety Monitoring Plan and/or the protocol document..

The general responsibilities for each External Site may include but are not limited to:

- Document the delegation of research specific activities to study personnel.
- Commit to the accrual of participants to the protocol.
- Submit protocol and/or amendments to their IRB of record. For studies under a single IRB, the Coordinating Center will facilitate any study-wide submissions..
- Maintain regulatory files as per ICH GCP and federal requirements.
- Provide the Coordinating Center with regulatory documents or source documents as requested.
- Participate in protocol training prior to enrolling participants and throughout the trial as required.
- Update Coordinating Center with research staff changes on a timely basis.
- Register participants through the Coordinating Center prior to beginning research related activities when required by the sponsor.
- Submit Serious Adverse Event (SAE) reports to sponsor, Coordinating Center, and IRB of record as applicable, in accordance with DF/HCC requirements.
- Submit protocol deviations and violations to the Sponsor, Coordinating Center, and IRB of record as applicable..
- Order, store and dispense investigational agents and/or other protocol mandated drugs per federal guidelines and protocol requirements.
- Participate in any quality assurance activities and meet with monitors or auditors at the conclusion of a visit to review findings.
- Promptly provide follow-up and/or corrective action plans for any monitoring queries or audit findings.

- Notify the sponsor immediately of any regulatory authority inspection of this protocol at the External Site.

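### Section 5.11 keeps unblinded interim results from the investigators, yet makes the Sponsor-Investigator their primary reviewer without limiting the report to threshold met or not met

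*Combined protocol and SAP*

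**What the plan says.** Section 5.11 (Requests for Unblinding) makes three statements about the futility look:

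- On the investigators: "The unblinded results of interim analyses will not be shared with the investigators prior to the completion of the study".
- On the codes: "Subject-level unblinding will be restricted to an unblinded statistician and scientific programmer performing the futility analysis".
- On review: "The Sponsor-Investigator will serve as the primary reviewer of the results of the interim analysis". This person is to act within the guidance laid down in the protocol when "making a decision on discontinuation of the study or modification".

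Section 13.4 sets the look at about 45 patients enrolled and treated in the randomized part, with 15 PFS events. The rule is: "If the observed hazard ratio (INT vs. INP) from the latency portion of the model is 0.96 or larger", enrolment stops and the trial ends for futility. The section names no body to receive this result. For the neurotoxicity rule, by contrast, it names the DSMB or DSMC.

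Under 12.2 the DSMB "will review and monitor study progress, toxicity, safety and other data from the randomized portion of this study", and "The DSMB will meet twice a year to review accrual, toxicity, response and reporting information". Appendix B, 2.1 (External Site), describes outside institutions as "collaborating with DF/HCC on a protocol where the sponsor is a DF/HCC investigator".

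On a related matter, 5.11 lets patients or treating investigators ask for the assignment on Day 365. Section 5.9 has standard-of-care tumor assessments captured over Days 421-589, and 11.6 does not require central review.

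**The concern.** The first and third statements in 5.11 do not fit together as written. The Sponsor-Investigator is an investigator (Appendix B) with continuing roles in conduct: under 5.5 this person is consulted on a second steroid-treated edema episode, and under 5.7 approves on-study brain surgery. The only restriction with a named boundary concerns patient-level codes. A hazard ratio of INT against INP lies outside that boundary.

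If the trial continues, its lead could hold a comparative efficacy estimate while half of the randomized patients have yet to enrol. That could affect enthusiasm for enrolment, trial conduct, and any change made under the undefined power of modification. Such a disclosure cannot be undone, so the wording matters before the look takes place.

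The Day 365 provision raises a smaller question of the same kind. Some progression feeding the primary PFS analysis could be read locally after a patient's assignment is known.

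**Working it through.** **1. The texts side by side.**

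| Question | What the plan states |
|---|---|
| Who is barred from unblinded results? | The investigators (5.11) |
| Who reviews the interim results? | The Sponsor-Investigator (5.11), an investigator per Appendix B, 2.1 |
| What is restricted by name? | Subject-level codes (5.11) |
| What is the result? | An arm-level latency hazard ratio (13.4) |
| Is the report limited to met or not met? | Not stated |
| What actions are defined for this look? | Stopping only (13.4); 5.11 adds modification without a rule |
| DSMB role in the futility look? | Neither stated nor excluded (12.2, 13.4) |

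A report limited to met or not met would reconcile the statements, but the plan does not say that this is what is sent.

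**2. Exposure at the look.** Patients still to enrol: 90 − 45 = 45.

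**3. Precision of what could be seen.** Inputs: 15 events and threshold 0.96 (13.4); design hazard ratio 0.557 (13.2). Treating the latency log hazard ratio as a Cox log hazard ratio with equal allocation:

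- SE = 2/√15 = 0.516. Estimating the cure part as well would, if anything, widen it.
- 95% interval around an observed 0.96: 0.96 × exp(±1.96 × 0.516) = 0.35 to 2.64.
- P(observed < 0.96) = Φ[(ln 0.96 − ln HR)/0.516]. This is 0.85 for a true HR of 0.557 and 0.47 for a true HR of 1.
- Given continuation at 0.557, the 5th, 50th and 95th percentiles of the observed value are 0.23, 0.51 and 0.88.

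A bare continue message reveals only that the estimate is below 0.96. These figures describe noise in the estimate; they do not measure bias.

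**4. Day 365 (minor).** Inputs from 13.2: cure fractions 0.30 (INP) and 0.50 (INT), hazard ratio 0.557, accrual over 24 months plus 12 months of follow-up, and 45 patients per arm. The plan's own figures first: cure odds ratio (0.5/0.5)/(0.3/0.7) = 2.33, as stated. With 0.6 as the marginal INP 6-month PFS, λ = ln(7/3)/6 = 0.1412 per month, and INT 6-month PFS = 0.5 + 0.5 × (3/7)^0.557 = 0.81, against a stated value of about 0.8.

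Expected events per arm between times a and b are 45 × ∫(1−c)λh·exp(−λht)·G(t)dt. Here c is the cure fraction and h is 1 (INP) or 0.557 (INT). G(t) is the share still under follow-up: 1 up to 12 months, then (36−t)/24. If 0.6 is instead the uncured patients' 6-month PFS, λ = −ln(0.6)/6 = 0.0851; this gives INT 0.88, a poorer match to 0.8.

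| Reading of 0.6 | Events to Day 589 | Days 365-589 | Days 337-589 |
|---|---|---|---|
| Marginal | 46.0 | 6.6 (14%) | 8.05 (17.5%) |
| Uncured only | 37.7 | 7.8 (21%) | 9.3 (25%) |

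The last column matters because progression is dated by scan. The last scheduled scan is at Day 337 (Section 10), so progression arising in Days 337-365 may first be read after Day 365. That adds about 1.5 events under either reading.

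**The case against.** The strongest reply is that 5.11 is coherent if the investigators means those at the sites. The preceding sentences concern blinding at the investigational sites, and the protocol uses Sponsor-Investigator and treating investigator as separate terms. On that reading, a sponsor role applies a fixed rule and the sites stay blind. This is possible, but the text does not state it. Even if accepted, it leaves open whether the Sponsor-Investigator sees the estimate or only the outcome of the rule.

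Other parts of the reply stand and limit the point:

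- A reader might infer that the Sponsor-Investigator may decide freely. The documents do not support that: 5.11 ties the decision to protocol guidance, and 13.4 makes stopping mandatory at 0.96 or above. Only the mention of modification leaves room.
- A reader might infer that individual progression calls would be biased by the interim look. They would not be exposed in that way, because patients' arms remain masked. Nor does anything show that a leak will occur; the defect is that the plan does not prevent one.
- A reader might infer that the DSMB is shut out. Its remit in 12.2 is broad enough to include futility, but no role is stated.
- This is a signal-detection phase II trial with one futility look and no early stopping for efficacy, which lowers the stakes.

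Day 365 elective unblinding is an openly stated choice made after study drug ends on Day 337, and no uptake is given. It is a separate and optional matter.

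**Conclusion.** The point holds as a gap in the plan's wording. Section 5.11 does not stop the trial lead from seeing an arm-level estimate, resting on about 15 events (SE of the log hazard ratio about 0.52 under a Cox approximation), while about 45 of up to 90 randomized patients are still to enrol. The exposure is to enrolment, conduct and any modification. No bias can be quantified from the documents, and no sample size, alpha or power figure changes.

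The Day 365 matter is minor. If every patient were unblinded, roughly 14% to 25% of PFS events to Day 589 could be read after Day 365. It is tempting to treat 14% as a ceiling, but it depends on reading 0.6 as marginal and on ignoring progression that arises after the Day 337 scan. Even 25% is not a strict bound: it rests on the design assumptions and stops at Day 589. In the other direction, the counts include deaths, which are not a matter of reading. It is also tempting to say that 6-month PFS is untouched because Day 365 comes later. If the 6-month estimates in 13.5 are taken from the fitted cure model, late events could move them slightly through the cure and latency parameters.

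**What to change.** **Main change, in 5.11 and 13.4 (with a matching line in 12.2).**

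- The unblinded statistician reports the futility result to the existing DSMB, ad hoc if the trigger falls between its twice-yearly meetings.
- The Sponsor-Investigator receives only threshold met or not met (stop or continue), with no effect estimate. At minimum, 5.11 should state that limit in one sentence.
- The reference to modification is deleted or tied to a stated rule, since 13.4 defines only stopping for this look.

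The cost is protocol wording and possibly one extra DSMB review. The ad hoc provision matters: waiting up to 6 months at about 3 patients per month could mean 6 × 3 = 18 further enrolments if accrual continues.

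**Optional addition.** Keep the Day 365 provision, record the date of each elective unblinding on the CRF, and add to 13.5 a supportive sensitivity analysis that censors PFS at that date. First reconcile the censoring rules: 11.5 uses the last disease evaluation, while 13.1 uses the last follow-up visit. Censoring at unblinding may be informative if requests follow suspected progression or plans for further therapy, so this analysis should support the primary analysis and not replace it. A documented PFS event should not be made the condition for unblinding, because that would create an incentive to call progression. Emergency unblinding is unchanged. The cost is one CRF date and one extra analysis.

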6. DOSING DELAYS/DOSE MODIFICATIONS

6.1 General considerations

The descriptions and grading scales found in the revised NCI Common Terminology Criteria for Adverse Events (CTCAE) version 5.0 will be utilized for dose delays and dose modifications. A copy of the CTCAE version 5.0 can be downloaded from the CTEP website http://ctep.cancer.gov/protocolDevelopment/electronic_applications/ctc.htm.

Dosing interruptions are permitted in the case of medical / surgical events or logistical reasons not related to study therapy (e.g., elective surgery, unrelated medical events, patient vacation, and/or holidays) and do not constitute a protocol violation. Subjects should be placed back on study therapy within 4 weeks of the missed dose, unless otherwise discussed with the study PI. The reason for interruption should be documented in the patient's study record. The maximum dose interruption of the checkpoint inhibitors (no administrations) for any reason is 84 calendar days (12 weeks). The maximum dose interruption of the Troriluzole for any reason is 42 calendar days (6 weeks). Missed doses are not to be made up; efforts will be made to get the patient back on the original schedule so that assessments are uniform across subjects.

For AEs unrelated to study drug(s), therapy may be held/resumed at the discretion of the treating investigator. Treatment-emergent AEs should continue to be monitored during the follow-up period (until resolution). New AEs during follow up that are not related to treatment should not be recorded

6.2 Dose Limiting Toxicities

For patients participating in the safety run-in, the following definition of dose-limiting toxicities (DLT) will be used:

The occurrence of any AE that meets all three of the following criteria:

1. Grade ≥ 3 toxicity **or** select grade 2 neurologic toxicity lasting 4 days or more, with or without medical intervention:
 - Ataxia
 - Central nervous system necrosis (use this term for radiation necrosis)

- Cognitive disturbance
 - Concentration impairment
 - Depressed level of consciousness
 - Dizziness
 - Encephalopathy
 - Guillain-Barre syndrome
 - Headache
 - Intracranial hemorrhage
 - Ischemia cerebrovascular
 - Leukoencephalopathy
 - Memory impairment
 - Presyncope
 - Reversible posterior leukoencephalopathy syndrome (PRES)
 - Stroke
 - Somnolence
- Confusion (categorized under Psychiatric disorders)
2. Occurred during the DLT evaluation period (i.e., occurred during the first 6 weeks of therapy), and
 3. Judged by the treating investigator to be possibly, probably or definitely related to troriluzole. Grade ≥ 3 toxicities that are related to ipilimumab and/or nivolumab but are unlikely related or not related to troriluzole are not considered DLTs. See Section 6.7 for list of Overlapping toxicities (“shared AEs”). Troriluzole therapy will be continued if there is an interruption in checkpoint therapy due to AE, and the AE is unlikely related or unrelated to troriluzole. Troriluzole and corticosteroids can be taken concurrently.

6.3 Troriluzole

General

Troriluzole therapy will be continued if there is an interruption in checkpoint therapy due to AE, and the AE is unlikely related or unrelated to troriluzole. Troriluzole and corticosteroids can be taken concurrently. Nivolumab and/or ipilimumab may still be given if Troriluzole is held or discontinued, if AE is unlikely related or unrelated to the checkpoint inhibitor treatments.

The maximum amount of time that troriluzole can be held continuously is 6 weeks. If the patient cannot resume troriluzole within 6 weeks, the patient will be removed from the study.

If a participant experiences multiple adverse events and there are conflicting recommendations, the investigator should use the recommended dose adjustment that reduces the dose to the lowest level.

Holding criteria

Troriluzole vs. placebo will be omitted and dose reduced for related AEs as follows.

Grade 1

For grade 1 events, dose holding is not required. If the grade 1 toxicity is intolerable to the patient, the drug may be held for 1 week at a time without lowering the dose. If drug is held for >1 week at a time, drug will be dose-reduced **one** level upon resumption. The intolerable nature of the AE must be documented as the reason for holding drug.

Grade 2

For grade 2 events, dose holding is required. When troriluzole is interrupted for an AE, the toxicity should be continually reassessed until it improves to Grade ≤ 1 , on approximately a weekly basis, which can be done remotely by telephone and/or lab assessment. If patient is able to resume drug ≤ 1 week, drug will be continued at the same dose, or, at the discretion of the treating investigator, it may be dose-reduced. If drug is held for >1 week at a time, it should be dose-reduced one level upon resumption. If grade 2 AE meets criteria for DLT (see section 6.2), troriluzole should be dose-reduced one level upon resumption.

Grade 3

For grade 3 events, dose holding is required. When troriluzole is interrupted for an AE, the toxicity should be continually reassessed until it improves to Grade ≤ 1 , on approximately a weekly basis, which can be done remotely by telephone and/or lab assessment. If the treating investigator believes permanent discontinuation is in the best interest of the patient (e.g. anaphylaxis), Troriluzole may be permanently discontinued after a discussion between the treating investigator and principal investigator. If the patient is able to resume drug, drug will be dose-reduced **one level**.

Grade 4

For grade 4 events, dose holding is required. When troriluzole is interrupted for an AE, the toxicity should be continually reassessed until it improves to Grade ≤ 1 , on approximately a weekly basis, which can be done remotely by telephone and/or lab assessment. If the treating investigator believes permanent discontinuation is in the best interest of the patient (e.g. anaphylaxis), troriluzole may be permanently discontinued after a discussion between the treating investigator and principal investigator. If the patient is able to resume drug, drug will be dose-reduced **two levels**.

Troriluzole vs. Placebo Dose Reductions

No specific management is indicated when troriluzole vs. placebo is held, other than supportive care. When therapy resumes, the dose must be reduced by one level per the table below. The maximum number of dose reductions is 2 as shown in the following de-escalation table.

Dose reductions for troriluzole

Dose Level	Troriluzole vs. Placebo Dose
0	140 mg PO QAM and 280 mg PO QPM
-1	140 mg PO BID
-2	140 mg PO daily

Intra-participant dose reescalation. Intra-participant dose reescalation is allowed. At the discretion of the treating physician, a patient who has previously been dose-reduced may re-escalate up to the starting dose. No patient should take more than the starting dose (Cohort 0). For example, if a AE improves with additional supportive measures (antiemetics, etc), or an alternate cause of the AE is identified, the physician and patient may opt to re-escalate.

